#### **4.2.2. Adherence to Study Drug**

A summary of adherence to study drug will not be provided.

A by-subject listing of study drug administration will be provided by subject ID number (in ascending order) and visit (in chronological order).

#### **4.3. Protocol Deviations**

A by-subject listing will be provided for those subjects who did not meet at least 1 eligibility (inclusion or exclusion) criterion. The listing will present the eligibility criterion (or criteria if more than 1 deviation) that subjects did not meet and related comments, if collected.

## 5. BASELINE CHARACTERISTICS

### 5.1. Demographics

Subject demographic variables will be summarized by treatment group and overall using descriptive statistics for continuous variables, and using number and percentage of subjects for categorical variables. The summary of demographic data will be provided for the Safety Analysis Set for the following:

- age (on the first dose date of any study drug) as a continuous variable
- sex at birth (male, female)
- race
- ethnicity (Hispanic or Latino, not Hispanic or Latino)
- country

A by-subject demographic listing, including the informed consent date, will be provided by treatment group and subject ID number in ascending order.

### 5.2. Other Baseline Characteristics

Other baseline characteristics include:

- height (cm)
- weight (kg)
- body mass index (BMI; in kg/m^2)
- swollen joint count based on 66 joints (SJC66) and tender joint count based on 68 joints (TJC68)
- HAQ-DI
- patient's pain assessment
- DAS28(CRP)
- patient's global assessment of disease activity
- physician's global assessment of disease activity
- Simplified Disease Activity Index (SDAI) and Clinical Disease Activity Index (CDAI)

- SF-36 (physical component summary score and mental component summary score)
- CRP (mg/L)
- stratification factor (DAS28[CRP] > 5.1 or DAS28[CRP] > 3.2 and  $\leq$  5.1; prior number of RA biologics used < 3 or  $\geq$  3)
- duration of RA (years)

duration of RA (years) = ((first dose date) – (date of initial diagnosis) + 1 day) / 365.25.

If the date of initial diagnosis is incomplete, then the following rules will be applied:

— missing day: use the first of the month.

— missing month: use January.

These baseline characteristics will be summarized by treatment group and overall using descriptive statistics for continuous variables and using number and percentage of subjects for categorical variables. The summary of baseline characteristics will be provided for the Safety Analysis Set.

A by-subject listing of other baseline characteristics will be provided by treatment group and subject ID number in ascending order.

### **5.3. Medical History**

The summaries of medical history will not be provided.

## 6. EFFICACY ANALYSES

### 6.1. General Considerations

The primary analysis set for efficacy analyses will be the FAS, defined in Section 3.1.2.

If multiple valid, nonmissing efficacy measurements exist in an analysis window, records will be chosen based on the following rules if a single value is needed:

- The record closest to the nominal day for that visit will be selected
- If there are 2 records that are equidistant from the nominal day, or more than 1 record (with time known) on the selected day, the latest record will be taken
- If chronological order cannot be determined (eg, more than 1 record on the same day with time missing), the worst scenario will be selected

#### 6.1.1. Tender/Swollen Joint Counts (TJC/SJC)

TJC68 and SJC66 will be collected during the course of the study. The assessment for each joint will be from the following selections: Tender Only, Swollen Only, Tender and Swollen, Not Tender or Swollen, or Joint Non-Evaluatable or Missing.

Individual joint with missing assessment will not be imputed. If at least half of the joints are assessed at a given visit, the *prorated* tender and swollen joint counts will be calculated using the following formula:

$$TJC68 = \frac{\text{Total number of tender joints}}{68 - (\text{Number of nonevaluatable or missing joints out of 68 joints})} \times 68$$

$$SJC66 = \frac{\text{Total number of swollen joints}}{66 - (\text{Number of nonevaluatable or missing joints out of 66 joints})} \times 66$$

If less than half of joints are assessed at a given visit, joint counts are treated as missing for that visit.

A more abbreviated assessment considering 28 joints as listed in Table 6-1 for both tenderness and swelling will also be conducted (as part of the TJC68 and SJC66 assessment), denoted as TJC28 and SJC28, respectively.

**Table 6-1. Composition of the 28 Joints**

Joints	Number
Shoulder Joints (Left and Right)	2
Elbow Joints (Left and Right)	2
Wrist Joints (Left and Right)	2
Metacarpophalangeal Joints I-V (Left and Right)	10
Proximal Interphalangeal Joints I-V (Left and Right)	10
Knee Joints (Left and Right)	2

If there are non-evaluable or missing joints among the 28 joints, similar prorated tender and swollen joint counts will be calculated as follows:

$$TJC28 = \frac{\text{Total number of tender joints}}{28 - (\text{Number of nonevaluable or missing joints out of 28 joints})} \times 28$$

$$SJC28 = \frac{\text{Total number of swollen joints}}{28 - (\text{Number of nonevaluable or missing joints out of 28 joints})} \times 28$$

If less than half of the 28 joints are assessed at a given visit, TJC28 and SJC28 are treated as missing for that visit.

### **6.1.2. Global Assessment of Disease Activity**

The Patient's Global Assessment of Disease Activity is a horizontal (0 – 100) visual analog scale (VAS) that ranges from "No Arthritis" to "Severe Arthritis."

The Physician's Global Assessment of Disease Activity is a horizontal (0 – 100) VAS that ranges from "No Disease Activity" to "Maximum Disease Activity."

## **6.2. Primary Efficacy Endpoints**

### **6.2.1. Definition of the Primary Efficacy Endpoints**

The primary endpoint for the study is change from baseline in DAS28(CRP) at Week 12. The DAS28(CRP) score is calculated as follows:

$$DAS28(CRP) = 0.56\sqrt{TJC28} + 0.28\sqrt{SJC28} + 0.36 \ln(CRP + 1) + 0.014 \times PtGA + 0.96,$$

where

TJC28 = number of joints tender out of 28 joints

SJC28 = number of joints swollen out of 28 joints

CRP = CRP measurement in unit of mg/L

PtGA = patient's global assessment of disease activity on a 0-100 VAS

Higher DAS28(CRP) value indicates more severe disease activity.

DAS28(CRP) will be calculated only for the time points with all measurements available, ie, missing DAS28(CRP) components will not be imputed.

#### **6.2.2. Statistical Hypotheses for the Primary Efficacy Endpoints**

No statistical hypotheses will be tested due to early termination of the study.

#### **6.2.3. Analysis of the Primary Efficacy Endpoint**

Due to early termination of the study by the sponsor, no formal statistical testing is planned for the final analysis. Primary efficacy endpoint data will be summarized using descriptive statistics by treatment group and visit.

### **6.3. Secondary Efficacy Endpoints**

The secondary efficacy endpoints are:

- Proportion of subjects that achieve  $\text{DAS28(CRP)} \leq 3.2$  at Week 12
- Proportion of subjects that achieve  $\text{DAS28(CRP)} < 2.6$  at Week 12
- Plasma concentrations of andecaliximab

#### **6.3.1. Analysis Methods for Secondary Efficacy Endpoints**

Due to the early termination of the study, no formal statistical testing is planned for the final analysis. Secondary efficacy endpoint data will be summarized using descriptive statistics by treatment group and analysis visit. The plasma concentrations of andecaliximab were not collected and will not be analyzed.

### **6.4. Exploratory Efficacy Endpoints**

#### **PPD**

#### **6.4.1. Definition of Exploratory Efficacy Endpoints**

##### **6.4.1.1. SDAI and CDAI**

##### **PPD**

##### **6.4.1.2. Health Assessment Questionnaire Disability Index (HAQ-DI)**

The HAQ-DI score is defined as the average of the scores of eight functional categories (dressing and grooming, arising, eating, walking, hygiene, reach, grip, and other activities), administered by the patient. Responses in each functional category are collected as: without any difficulty; with some difficulty; with much difficulty; unable to do a task in that area; and with or without aids or devices. The HAQ-DI score ranges from 0 (no disability) to 3 (completely disabled), when 6 or more categories are non-missing. Detailed algorithm for calculating HAQ-DI score is described in Appendix 1.

The HAQ-DI also includes a separate pain assessment and the subject will be requested to mark the severity of the pain in the past week on a 0-100 VAS, with 0 indicating “no pain” and 100 indicating “severe pain.”

##### **6.4.1.3. 36-Item Short-form Health Survey**

The SF-36 (version 2) is a health related quality of life instrument consisting of 36 questions belonging to 8 domains in 2 components and covers a 4-week recall period:

- Physical component: 4 domains: physical functioning (10 items), role physical (4 items), bodily pain (2 items), and general health perceptions (5 items)
- Mental component: 4 domains: vitality (4 items), social functioning (2 items), role emotional (3 items), and mental health (5 items).

The physical component and mental component will be scored and presented.

**6.4.2. Analysis Methods for Exploratory Efficacy Endpoints**

**PPD**

## 7. SAFETY ANALYSES

### 7.1. Adverse Events and Deaths

#### 7.1.1. Adverse Event Dictionary

Clinical and laboratory adverse events (AEs) will be coded using the current version of the Medical Dictionary for Regulatory Activities (MedDRA). System organ class (SOC), high-level group term (HLGT), high-level term (HLT), preferred term (PT), and lower-level term (LLT) will be provided in the AE dataset.

#### 7.1.2. Adverse Event Severity

Adverse events are graded by the investigator as Grade 1, 2, 3, 4, or 5 according to toxicity criteria specified in the protocol. The severity grade of events for which the investigator did not record severity will be categorized as “missing” for tabular summaries and data listings. The missing category will be listed last in summary presentation.

#### 7.1.3. Relationship of Adverse Events to Study Drug

Related AEs are those for which the investigator selected “Related” on the AE CRF to the question of “Related to Study Treatment.” Relatedness will always default to the investigator’s choice, not that of the medical monitor. Events for which the investigator did not record relationship to study drug will be considered related to study drug for summary purposes. However, by-subject data listings will show the relationship as missing.

#### 7.1.4. Serious Adverse Events

Serious adverse events (SAEs) will be identified and captured as SAEs if AEs met the definitions of SAE specified in the study protocol. SAEs captured and stored in the clinical database will be reconciled with the SAE database from the Gilead Drug Safety and Public Health (DSPH) Department before data finalization.

#### 7.1.5. Treatment-Emergent Adverse Events

##### 7.1.5.1. Definition of Treatment-Emergent Adverse Events

Treatment-emergent adverse events (TEAEs) are defined as one or both of the following:

- Any AEs with an onset date on or after the study drug start date and no later than 30 days after permanent discontinuation of study drug
- Any AEs leading to premature discontinuation of study drug

#### 7.1.5.2. Incomplete Dates

If the onset date of the AE is incomplete and the AE stop date is not prior to the first dosing date of study drug, then the month and year (or year alone if month is not recorded) of onset determine whether an AE is treatment emergent. The event is considered treatment emergent if both of the following 2 criteria are met:

- The AE onset is the same as or after the month and year (or year) of the first dosing date of study drug, and
- The AE onset date is the same as or before the month and year (or year) of the date corresponding to 30 days after the date of the last dose of study drug

An AE with completely missing onset and stop dates, or with the onset date missing and a stop date later than the first dosing date of study drug, will be considered to be treatment emergent. In addition, an AE with the onset date missing and incomplete stop date with the same or later month and year (or year alone if month is not recorded) as the first dosing date of study drug will be considered treatment emergent.

#### 7.1.6. Summaries of Adverse Events and Deaths

Treatment-emergent AEs will be summarized based on the Safety Analysis Set.

The AEs will be reported by the treatment period. If subject does not continue into the OLE then all TEAEs will be reported in the DB treatment period (Day 1 to Week 12) summaries. For subjects who continue into the OLE, TEAEs during the DB treatment period are the AEs that started prior to the first dose of OL treatment. The AEs with the onset date on or after the first dose of the OL treatment and no later than 30 days after permanent discontinuation of study drug will be reported in the OLE summaries.

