 - a) Carcinoma in situ of the cervix that has been successfully treated
 - b) Adequately treated basal or squamous cell cancer that has been successfully treated

Study Procedures/
Frequency:

All subjects will have the following visits at the study site during the blinded period of the study: Screening, Day 1 (first dose of study drug) and Weeks 1, 4, 8 and 12. Subjects will receive the first two injections of study drug (Day 1 and Week 1) at the study site. After completion of the 12 week blinded period of the study, subjects will have the option to participate in the OLE in the same protocol. Subjects who do not participate in the OLE will complete Week 12 assessments and will not receive open label study drug. These subjects

will have a follow up visit 30 days after their last dose of study drug.

Subjects who are eligible will receive their first dose of OLE study drug at Week 12, after completing all the required assessments of the Week 12 visit. Additional OLE study visits will occur at Weeks 13, 19, 24, 30, 36, 42, 48, 54, 60, and 64, with a follow-up visit 30 days after the subject's last dose of study drug.

Screening Assessments

- Confirmation of RA diagnosis
- Medical/Surgical history
- Vital signs to include blood pressure, pulse, temperature and respiration
- Complete physical exam (CPE) height and weight
- 12 lead ECG
- Central laboratory tests including Rheumatoid Factor, anti-CCP, complete blood count, hematology, chemistry panel, urinalysis, urine drug screen, serum β -HCG (women of childbearing potential), QuantiFERON® TB-Gold In-Tube test, HIV, Hepatitis B and C testing (with reflex testing if positive for antibodies), CRP, Estimated Glomerular Filtration Rate (based on MDRD study equation), TSH and HbA1c. Flow cytometry for absolute CD19+ B-cell counts (subjects who have taken rituximab or any B cell depleting agent)
- A negative chest X-ray (views per local guidelines) for active lung disease at Screening; or a chest X-ray within 90 days of Screening if films and/or report are available for investigator review.
- 66 swollen and 68 tender joint counts
- Patient's and Physician's Global Assessment of Health
- Patient's Assessment of Pain

On-Treatment Assessments

- Concomitant medications
- Vital signs to include blood pressure, pulse, temperature, respiration, and weight
- CPE (Blinded period Week 12 and Week 64 only); targeted Physical exam (TPE) at all other visits
- 12-lead ECG (Week 12 blinded period and Week 64 only)

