3.4. Duration of Treatment

Subjects will receive 12 SC injections of weekly study drug (GS-5745 or placebo) in the blinded period and up to 53 weekly doses of GS-5745 in the OLE.

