- q Subjects not participating in the OLE will complete all week 12 assessments but will not receive an injection of study drug at the Week 12 visit. If subjects are eligible to participate in the OLE, then subjects complete all Week 12 assessments for the blinded period and then receive the first dose of the drug for OLE.
- r Study drug for 4 weekly doses will be dispensed at Weeks 1, 4 and 8
- s If not done in the prior 12 weeks. ECGs are to be performed supine
- t Per discretion of investigator

Study Visits: Open Label Extension														
Week	12	13	19	24	30	36	42	48	54	60	64	30 Day Follow Up	Unscheduled Visit ^k	ESDD
Window in Days	±3	±3	±5	±5	±5	±5	±5	±5	±5	±5	±5	±5		±3
Complete physical exam												X		
Targeted physical exam ^b		X	X	X	X	X	x	X	X	X	X	X	X	X
Vital signs and weight ^a		X	X	X	X	X	X	X	X	X	X	X	X	X
12 lead ECG											X		X ^k	
66 swollen and 68 tender joint count assessment				X		X		X		X	X	X	X ^k	X
Disease Specific Questionnaires and Activity Scales				X		X		X		X	X	X	X ^k	X
HAQ-DI				X		X		X		X	X	X	X ^k	X
SF-36				X		X		X		X	X	X	X ^k	X
Hematology ^c		X	X	X	X	X	X	X	X	X	X	X	X	X
Chemistry panel ^c		X	X	X	X	X	X	X	X	X	X	X	X ^k	X
Urinalysis		X	X	X	X	X	X	X	X	X	X	X		X
Erythrocyte Sedimentation Rate (ESR) Local lab			X	X	X	X	X	X	X	X	X	X		X
serum β-HCG Pregnancy Test ^d												X		X

Study Visits: Open Label Extension														
Week	12	13	19	24	30	36	42	48	54	60	64	30 Day Follow Up	Unscheduled Visit ^k	ESDD
Window in Days	±3	±3	±5	±5	±5	±5	±5	±5	±5	±5	±5	±5		±3
Urine Pregnancy test at study visits as marked – and every 4 weeks using kit at home (at weeks 16, 20, 28, 32, 40, 44, 52, and 56) ^d				X		X		X		X	X		X	
PK collection ^e				X							X			X
GS-5745 ADA collection ^f			X								X	X		
Biomarker collection	X			X		X		X		X				
C-Reactive Protein (hsCRP)		X	X	X	X	X	X	X	X	X	X	X	X	X
QuantiFERON-GOLD (QFT)									X					X
Chest x-ray (based on local TB screening guidelines)									X					
Estimated Glomerular Filtration Rate (based on MDRD study equation) performed at central lab				X		X		X		X				X

Study Visits: Open Label Extension														
Week	12	13	19	24	30	36	42	48	54	60	64	30 Day Follow Up	Unscheduled Visit ^k	ESDD
Window in Days	±3	±3	±5	±5	±5	±5	±5	±5	±5	±5	±5	±5		±3
Study Drug Dispensing ^g	X		X	X	X	X	X	X	X	X	no			
Study Drug Administration ^h														
Concomitant medications ⁱ	X	X	X	X	X	X	X	X	X	X	X	X	X	
Adverse Events ⁱ	X	X	X	X	X	X	X	X	X	X	X	X	X	

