#### 4.2.1. Duration of Exposure to Study Drug

Total duration of exposure to any study drug will be defined as (last dose date of any study drug - first dose date of any study drug + 1), regardless of any temporary interruptions in study drug administration and will be expressed in weeks using up to 1 decimal place (eg, 4.5 weeks).

If the last study drug dosing date is missing, the latest date among the study drug end date, clinical visit date, laboratory sample collection date, weight and vital signs assessment date that occurred during the on-treatment period will be used.

The total duration of exposure to any study drug will be summarized using descriptive statistics and using the number (ie, cumulative counts) and percentage of subjects exposed through the following time periods: Baseline (Day 1), Week 1 (Day 8), Week 4 (Day 29), Week 8 (Day 57), and Week 12 (Day 85).

Summaries will be provided by treatment group for the Safety Analysis Set. No formal statistical testing is planned.

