#### **7.2.2.2. Summaries of Laboratory Abnormalities**

The summaries (number and percentage of subjects) for treatment-emergent laboratory abnormalities will be provided by lab test, treatment group and treatment period; subjects will be categorized according to the most severe postbaseline abnormality grade for a given lab test. If subject does not continue into the OLE then all treatment-emergent laboratory abnormalities will be reported in the DB treatment period (Day 1 to Week 12) summary. For subjects who continue into the OLE, treatment-emergent laboratory abnormalities during the DB treatment period are the laboratory abnormalities that started prior to the first dose of OL treatment. The laboratory abnormalities with the onset date on or after the first dose of the OL treatment and no later than 30 days after permanent discontinuation of study drug will be reported in the OLE summary.

A by-subject listing of treatment-emergent Grade 3 or higher laboratory abnormalities will be provided by subject ID number and visit in chronological order. This listing will include all test results that were collected throughout the study for the lab test of interest, with all applicable severity grades displayed.

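### Double-blind safety tables headed Day 1 to Week 12 run to last dose + 30 days for subjects who stay out of the open-label extension, but stop at the first open-label dose for those who enter it

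*SAP*

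**What the plan says.** SAP 7.1.5.1 counts an adverse event as treatment-emergent if it starts on or after first dose and "no later than 30 days after permanent discontinuation of study drug". Events leading to discontinuation also qualify.

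SAP 7.1.6 then assigns these events to periods by two different rules:

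- Subjects who do not continue into the OLE: "all TEAEs will be reported in the DB treatment period (Day 1 to Week 12) summaries".
- Subjects who continue: "TEAEs during the DB treatment period are the AEs that started prior to the first dose of OL treatment". Later events go to the OLE summaries.

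SAP 7.2.2.2 repeats the split for laboratory data. For subjects outside the OLE, "all treatment-emergent laboratory abnormalities will be reported in the DB treatment period (Day 1 to Week 12) summary". SAP 3.8.1 applies the same division to period outputs in general.

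The dosing calendar comes from the protocol. Section 3.4 says "Subjects will receive 12 SC injections of weekly study drug (GS-5745 or placebo) in the blinded period". Under Appendix 2, subjects not entering the OLE "will not receive an injection of study drug at the Week 12 visit". For the others, the synopsis says "Subjects who are eligible will receive their first dose of OLE study drug at Week 12".

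SAP 7.1.6.1 counts each subject once per summary, as a number and percentage. No person-time rate, common cut-off or follow-up column is specified for these tables.

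**The concern.** The heading promises one fixed period for everyone, but the rule supplies two. For a subject who stays out of the OLE, events that began after Week 12 and weeks after the last injection appear under a Day 1 to Week 12 label. For an OLE entrant the count ends before the first open-label dose.

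OLE entry follows randomisation. It is optional, open only to those who complete the blinded period, and closed to subjects withdrawn from the study after stopping drug (Protocol 6.5). It can therefore be related to tolerability. If arms differ in OLE entry, crude percentages compare arms with different observation time, and the arm with lower entry shows more events without any drug effect.

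These tables carry much of what remains of the secondary safety objective. The SAP has dropped all hypothesis testing, PK analysis, laboratory descriptive statistics, and summaries of vital signs and ECG.

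**Working it through.** **Inputs**

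- Treatment-emergent window: 30 days after last dose (SAP 7.1.5.1).
- Blinded doses: 12, weekly from Day 1 (Protocol 3.4).
- No Week 12 injection for subjects outside the OLE; first open-label dose at Week 12 for entrants (Protocol Appendix 2 and synopsis).
- Week 12 visit window: ±3 days (Protocol Appendix 2).

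**The plan's own days.** Nominal day = 1 + 7 × week. Week 8 gives 1 + 56 = Day 57 and Week 12 gives 1 + 84 = Day 85, both as in SAP 4.2.1.

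**Windows for a 12-dose completer**

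- Last blinded dose (Week 11): 1 + 7 × 11 = Day 78.
- Not entering the OLE: 78 + 30 = Day 108, so 108 days, ending 108 − 85 = 23 days after nominal Week 12.
- Entering the OLE: Day 85 − 1 = Day 84, so 84 days.
- Difference: 108 − 84 = 24 days. Ratio: 108/84 = 1.286, or 29% more time.
- With the first open-label dose on Day 82 or Day 88, and the last blinded dose held at Day 78: 108 − 81 = 27 days, or 108 − 87 = 21 days.

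**Early stoppers.** The window exceeds 84 days only if last dose day + 30 > 84, that is, a last dose on or after Day 55. On the weekly calendar, a last dose on Day 50 gives Day 80 (shorter than an entrant's window) and one on Day 57 gives Day 87 (longer).

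**Illustrative effect on incidence.** The documents give neither incidence nor OLE uptake, so every input here is an assumption. With a constant hazard and an 84-day incidence p, the 108-day incidence is 1 − (1 − p)^(108/84). A gap in OLE entry of 30 percentage points between arms multiplies the increase by 0.30.

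| p over 84 days | over 108 days | increase (points) | × 0.30 (points) |
|---|---|---|---|
| 10% | 12.7% | 2.7 | 0.8 |
| 20% | 24.9% | 4.9 | 1.5 |
| 30% | 36.8% | 6.8 | 2.0 |
| 40% | 48.1% | 8.1 | 2.4 |
| 50% | 59.0% | 9.0 | 2.7 |
| 60% | 69.2% | 9.2 | 2.8 |

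For incidences of 30% to 60% the artificial difference is about 2 to 3 points. With equal uptake it is zero between arms, although both percentages still exceed the true Week 12 figure.

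**Laboratory data.** Results come from scheduled draws, so the hazard calculation does not carry over. After baseline, hematology and chemistry are scheduled at Weeks 1, 4 and 12 and at the 30-day follow-up (Protocol Appendix 2). The excess is therefore at most about one scheduled draw.

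- Protocol 6.3.1 times the follow-up from the Week 12 visit: 85 + 30 = Day 115. That is after Day 108, so SAP 3.8.2 and 7.2.2.1 exclude it.
- The synopsis times it from the last dose: nominal Day 108, ±5 days. It counts only if it falls on or before last dose + 30.

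The laboratory tail may therefore be empty. The two follow-up timings need to be reconciled.

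**The case against.** The strongest defence is that each half of the rule is reasonable. The 30-day window is the protocol's own (8.6 and 8.6.2). Events soon after stopping drug can belong to blinded treatment, and Protocol 7.3 collects adverse events to 55 days after the last dose. Entrants have to be cut at the first open-label dose because all of them then receive 300 mg. This stands, and the point does not challenge the treatment-emergent definition. It does not explain why events after Week 12 belong in a column headed Day 1 to Week 12.

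The second defence is that the consequence is small, which also stands. The SAP plans no inferential analysis in the 15 enrolled subjects, lists every adverse event with a treatment-emergence flag, and summarises exposure by arm. With five subjects per arm (15/3, assuming 1:1:1 held), 2 to 3 points is 0.10 to 0.15 of a subject.

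A reader might infer more than the documents support:

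- *That subjects outside the OLE gain 30 extra days.* Entrants also contribute the first 6 days after Day 78 (Days 79 to 84), so the net difference is 24.
- *That early termination lengthens the window of everyone still in the blinded period.* It exceeds 84 days only with a last dose on or after Day 55.
- *That the arms are shown to be biased.* This needs OLE entry to differ by arm, and no uptake is reported. Termination for business reasons (SAP 1) also makes non-entry less a matter of response or tolerability.
- *That the laboratory tables are affected to the same degree.* They gain one scheduled draw at most.

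**Conclusion.** The point holds as a flaw in period assignment and labelling. For a 12-dose completer the double-blind tables cover nominally 108 days without OLE entry and 84 days with it, and the heading is wrong for the longer window whatever the uptake. The day counts follow from the documents, assuming doses and visits on nominal days; moving only the first open-label dose within its visit window gives a difference of 21 to 27 days.

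Bias between arms is conditional on unequal OLE entry, and its size cannot be derived from the documents. The 2-to-3-point figure rests on an assumed 30-point gap, a constant hazard and an 84-day incidence of 30% to 60%. Practical impact in this descriptive report is limited, but a change before database finalization is worthwhile because it is cheap and these tables are the main by-arm safety evidence left.

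**What to change.** Amend SAP 7.1.6 and 7.2.2.2 as follows:

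- Keep the treatment-emergent definition, and keep the cut at the first open-label dose for OLE entrants.
- For subjects not entering the OLE, count in the double-blind column only events with onset before the Week 12 visit date, or before nominal Day 85 if there is no such visit.
- Show their later treatment-emergent events, up to last dose + 30 days, in a separate post-treatment follow-up column.
- Apply the same rule to laboratory abnormalities, worded so that the Week 12 sample itself stays in the double-blind column for both groups. SAP Table 3-2 already lets the Week 12 window include the first open-label dose date.

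Completers in both groups then have a nominal 84-day window for adverse events, and every treatment-emergent event within last dose + 30 days has a column. SAP 3.8.2 already treats the 30-day follow-up visit as separate, so this extends an existing convention.

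A cut-off at last blinded dose + 7 days should not be used. An entrant last dosed on Day 78 whose first open-label dose is on Day 88 would have a cut-off of Day 85, and events starting on Days 86 or 87 would fall into no summary.

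The cost is two sentences in the SAP and one table column. The small downside is that a few delayed events of subjects outside the OLE move out of the double-blind column.
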